### **1.3.1 Tumor oxygenation is a critical factor in malignant cancer progression and therapy**

Based on data from the use of the Eppendorf technique and other studies, it has been concluded that the partial pressure of oxygen ( $pO_2$ ) in solid tumors is the most important parameter affecting clinical outcomes. Pretreatment  $pO_2$  level in solid malignancies, measured by oxygen electrodes, has been shown to be the most important determinant of the therapeutic response, especially to radiation therapy. This dependency on oxygen levels appears to be more significant than stage, tumor morphology, or tumor size. There are also data that indicate oxygen levels are very important factors in the response to surgical and chemotherapeutic approaches in addition to radiation therapy. For example, in squamous cell carcinomas (SCC) of both the head and neck and cervix. The oxygen level in tumors not only affects the response of tumors to therapy but also the malignant progression of tumors. This dependency of outcomes on oxygen levels may be related to the well-established observation that the level of oxygen can significantly affect the nature of the tumor, with hypoxia leading to more aggressive behavior of tumors through mechanisms that are being increasingly understood.

In addition to influencing treatment efficacy, oxygen levels of the tissues in the tumor bed can influence outcomes related to the morbidity of therapy. Information about  $pO_2$  at critical sites will be useful for enhancing treatment options to facilitate wound healing, and the utility of reconstructive tissue transplantation, especially when surgery and radiation are used in combination.

Oxygen levels in tumors change with time. These changes include those occurring across very short time scales related to underlying pathophysiology, those induced by tumor growth, and those induced by treatment itself. Therefore, it is very desirable to monitor the oxygen level in tumors before, during, and after therapeutic interventions. This requires a means to make direct and repeated measurements of oxygen in tissue at specific sites, a capability that is not available in the clinic. Achieving this capability would have very significant implications for improving cancer therapy across a patient's clinical course, from initial diagnosis to primary treatment to post-treatment morbidity.

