### 2.2 Secondary Objective

This study will also determine the feasibility of repeated measurements of oxygen in tumors using the OxyChip and EPR oximetry. This objective is unrelated to the primary safety objective.

- To assess the feasibility of making repeated measurements of tumor oxygen levels in patients with easily-accessible, superficial tumors.
- To determine the tumor oxygen levels in patients without therapy prior to surgical excision (Phase 1A), or during a course of radiotherapy or neoadjuvant chemotherapy prior to surgical excision (Phase 1B).
- To determine the workflow and time required for each daily oxygen measurement.

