This larger cohort will allow further assessment of safety, as well as optimization of procedures for the OxyChip placement and subsequent oxygen measurements for different tumor types in different anatomical locations. This expanded Phase 1 study will also achieve a secondary goal of increasing patient numbers for specific tumor types (*i.e.*, melanomas, squamous cell carcinomas and sarcomas) to assess the levels of tumor oxygenation and their response to supplemental oxygen breathing.

The phase 1B patients will have up to five oxygen measurements per week during the course of radiation or chemotherapy. Patients will be evaluated weekly during radiotherapy or prior to each chemotherapy administration or follow-up appointment for assessment of any adverse effects, as per the primary objective. Oximetry measurements will be taken periodically, from at least one day after implantation up to the OxyChip's removal. The OxyChip will be removed at a planned surgery as part of standard-of-care therapy. Phase 1A patients will be evaluated at least monthly prior to OxyChip removal for assessment of adverse effects, again for the primary objective.

If a patient cannot or does not return for an evaluation, the study team will contact the patient by phone or email to check for development of new adverse events or changes in health status. Assessments by non-study physicians or physician extenders as part of standard care are also an acceptable replacement, if the patient is not accessible for an in-person evaluation. Following resection, the tissue surrounding the OxyChip will be examined for any adverse effects, as per the primary objective. For the exploratory objectives, the tissue will also be examined for biomarkers associated with hypoxia or growth.

Schema:

PHASE 1A	
Purpose	
Primary: Safety of the OxyChip placement procedure and OxyChip removal after short duration (typically less than 4 weeks, but up to 52 weeks).
 
Secondary: Feasibility of taking repeated oxygen measurements using the OxyChip.

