	
will still be eligible for enrollment as long as a PI or Co-PI on the study can evaluate the implanted site at least every two weeks during treatment. Of note, patients must receive their surgery at DH to be eligible.
 
 
• Superficial tumors located <math>\leq 3</math> cm from skin or mucosal surface, where neoadjuvant radiotherapy or neoadjuvant chemotherapy followed by surgical resection is planned.
 
• Eligible tumor histology for this protocol is any biopsy proven malignancy expected to undergo neoadjuvant chemotherapy or radiotherapy prior to resection
 
• Previous radiation to the site is not allowed.
 
• Use of angiogenesis inhibitors is not allowed.
 
• Planned use of concurrent neoadjuvant chemoradiotherapy, or sequential neoadjuvant radiation therapy and chemotherapy, prior to resection, is not allowed.
 
• Patients do not have to agree to an oxygen measurement in order to be eligible. Although oxygen measurements are desirable, the primary endpoint is safety of OxyChip during neoadjuvant radiation or chemotherapy.
 
• Tumors must be <math>\geq 2.5</math> cm in minimum diameter to be eligible.
 

OxyChip placement	Placement of OxyChip will be through a minimally invasive procedure ( see methods for implantation protocol ).
OxyChip removal	The OxyChip will be removed with the tumor mass at the time of surgical resection and examined for adverse events (primary goal). Tumor tissue surrounding the implanted device will be collected and stored to allow for future evaluation of molecular biomarkers (exploratory goal).
Oxygen measurements	The goal is at least two measurements prior to the start of radiation therapy and then up to five times per week during radiotherapy or chemotherapy for the secondary objective. Note, however, that oxygen measurements are not necessary for the study's primary goal to determine the presence or absence of any adverse events after implantation of the OxyChip.

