#### 5.2.4 OxyChip and Fiducial removal

The OxyChip and fiducial(s) will be excised with the surgical specimen. The surgeon determines the timing of surgery, but it will typically be planned to be within 4 weeks for Phase 1A, or after completion of radiotherapy or chemotherapy for Phase 1B, although the OxyChip may remain implanted for up to 52 weeks for both Phases (excluding the first 6 patients enrolled into Phase 1A). The minimum time from implantation to surgical excision required for inclusion is 3 days. Note, patients in Phase 1B are expected to have the OxyChip in place for a minimum of 5 weeks (the expected duration of radiation therapy). The protocol and goals for removal will be as follows:

- (i) All attempts will be made to maintain the OxyChip in the tissue specimen, without disrupting the shape or position within the tumor mass.
- (ii) In collaboration with the surgeon, after the patient has been anesthetized, imaging of the fiducial(s) will occur prior to surgery in order to identify the putative location of the OxyChip and facilitate surgical removal.
  - a. We anticipate the fluoroscopy will be sufficient for identification of the fiducial prior to surgical removal (and after). However, due to concerns that more advanced imaging may be necessary, the first three patients with fiducial implantation will have their surgery performed at DHMC in the Center for Surgical Innovation (CSI). If fluoroscopy is sufficient for identification, then subsequent surgeries can be performed in standard operating rooms as desired if fluoroscopy is available for identification of fiducials before and after surgery.
    - i. In the first three patients in the CSI, if the fiducial is not found prior to surgery either CT or MRI imaging will be performed to identify the fiducials. If the fiducials are found within the expected surgical field, or reasonably adjacent, fiducials will be removed during surgery. If the fiducials are found in an unanticipated area, consultation between the PI and the surgeon will occur as to whether surgical resection is acceptable. All decisions regarding surgery will be at the discretion of the surgeon. If no fiducials are found after advanced imaging prior to surgery, then surgery will proceed as planned as all reasonable measures will have been taken to identify the location of the OxyChip at that time.

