### **5.3 Subject Compliance Monitoring**

Patients in Phase 1A will typically have the OxyChip implanted for a short duration ( $\leq 4$  weeks), but may remain for up to 52 weeks, and the patient will be seeing the surgeon for surgical planning and post-operative evaluations, making non-compliance unlikely. Phase 1A patients will be evaluated at least monthly prior to the OxyChip removal to check for any adverse events, as per the primary objective. Patients in Phase 1B will be receiving daily radiotherapy or a course of chemotherapy and therefore will be seen by a physician at least weekly or with each chemotherapy cycle for standard evaluation. At these appointments, the PI, co-investigators or staff protocol members perform safety monitoring by querying the patient about his or her local symptoms relating to the OxyChip implantation, and by inspection of the implantation site if possible, depending on the patient's willingness to allow inspection. Evaluation can also be performed at Norris Cotton Cancer Center North by one of the DH radiation or medical oncologists who are protocol staff, if the patients elects to receive radiation or chemotherapy at that facility prior to surgery (Phase 1B).

If the patient is unwilling to see the PI or co-investigators during a visit at which toxicity is to be assessed, or if the patient is unable to be seen due to logistical considerations, the patient by phone to evaluate potential toxicity. All efforts will be made to see the patient in clinic and perform an inspection of the implanted site. If the patient is receiving oxygen measurements, the patient will be seen by the EPR team at that time, ensuring compliance. It is possible that patients will decline oxygen measurements, but this will have a minor impact on the secondary objective (feasibility), and no impact on the primary objective (safety). Assessments by non-study physicians as part of standard of care are also an acceptable replacement if the patient is not accessible for an in-person evaluation.

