# 7 Statistical Plan

## 7.1 Statistical Methods

This is a first-in-humans pilot study/Phase I trial designed to (1) test the safety and toxicity of the OxyChip and patient tolerance of its presence and to (2) help design a larger confirmatory study. As such, the study was sequentially designed into different cohorts, as previously described in section\_3.1. The criteria for proceeding with each cohort is not based on statistical significance but on the presence and severity of any unexpected adverse events and whether they can be attributed to the OxyChip. The sample size was selected to be within the range recommended for early phase I trials.

For purposes of examining the secondary goal, the feasibility of using the OxyChip to assess PO2, we will use a qualitative assessment about whether any attempted measurements were successful, and assess the time for making measurements. Oxygen measurements will be averaged across visit days (if available) per subject for all subjects in Phase 1A and Phase 1B. We will use a paired t-test to detect statistically significant acute changes in pO2. To compare time period measurements per visit across patients, we will use an ANOVA model to account for individual variation of the baseline pO2. Finally, if the oxygen level exhibits a nonlinear pattern we will use a nonlinear fitting technique. To account for substantial variations of pO2 across patients, methods of repeated measurements and mixed modeling will be used.

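### For Phase 1B radiotherapy patients, the per-subject average in 7.1 mixes pre-course with on-course pO2, so it is not the on-course level that 2.2 sets out to determine

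*Combined protocol and SAP*

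**What the plan says.** The averaging rule is in 7.1: "Oxygen measurements will be averaged across visit days (if available) per subject for all subjects in Phase 1A and Phase 1B". It makes no distinction by treatment period.

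The Phase 1B schema in 3.1 sets the measurement goal for radiotherapy patients as "at least two measurements prior to the start of radiation therapy and then up to five times per week during radiotherapy". The general text of 3.1 sets the outer window: "Oximetry measurements will be taken periodically, from at least one day after implantation up to" removal of the device, which happens at surgery. A session after the last fraction but before surgery is therefore allowed.

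Section 2.2 lists, among the secondary aims, determining tumour oxygen levels without therapy in Phase 1A, "or during a course of radiotherapy or neoadjuvant chemotherapy prior to surgical excision (Phase 1B"). The background in 1.3.1 says that "it is very desirable to monitor the oxygen level in tumors before, during, and after therapeutic interventions", and counts among the sources of change over time "those induced by tumor growth, and those induced by treatment itself".

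The same paragraph of 7.1 also names a paired t-test for acute changes, an ANOVA of time periods per visit, nonlinear fitting, and repeated-measures or mixed models to handle variation across patients. None of these is given a term for course period.

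**The concern.** The rule in 7.1 gives each subject one averaged value. In Phase 1A, where no therapy precedes resection, that is a reasonable summary. In a Phase 1B radiotherapy patient the same rule puts untreated and treated sessions into one number. If treatment changes tumour pO2, as 1.3.1 says it does, the number estimates neither the pre-treatment level nor the level during the course. It is a weighted mix of the two, and the weights are set by how often the patient came for measurement.

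The description of on-course oxygenation in 2.2 is what is at stake. Patients with the same oxygenation but different attendance could get different averages. A group summary of such averages would carry attendance as well as physiology into the design of later studies, which 7.1 gives as one purpose of the trial.

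The schema states a pre-treatment measurement goal only for radiotherapy, so the point is confined to those patients.

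**Working it through.** The plan states no figure on this point, so there is nothing to reproduce. The check is how much of the 7.1 average comes from before the course.

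**Inputs**
- Pre-course sessions: 2, the minimum of the goal in the Phase 1B schema (3.1).
- Course length: 5 weeks, the expected duration of radiotherapy in 5.2.4.
- On-course sessions per week: up to five (3.1). Values from 1 to 5 are used, because the documents give only the ceiling.
- Post-course sessions: allowed by 3.1, number not given, set to zero here.

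**Formula.** With n on-course sessions, the pre-course share is w = 2/(2 + n).

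| On-course sessions per week | n over 5 weeks | All sessions | w |
|---|---|---|---|
| 1 | 5 | 7 | 2/7 = 28.6% |
| 2 | 10 | 12 | 2/12 = 16.7% |
| 3 | 15 | 17 | 2/17 = 11.8% |
| 5 | 25 | 27 | 2/27 = 7.4% |

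**Effect on the average.** Let P be the pre-course level, D the on-course level, and c = D - P. The 7.1 average is wP + (1 - w)D = D - wc, so it misses the on-course level by wc: 0.286c at one session a week, 0.167c at two and 0.074c at five. Two patients with identical P and D, one measured once a week and the other five times, differ by (0.286 - 0.074)c = 0.212c through attendance alone.

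**In mmHg.** The documents give no value for c. For illustration only, under assumed levels:
- P = 5, D = 10: the average is 8.6 at one session a week and 9.6 at five.
- P = 5, D = 15: the average is 12.1 and 14.3.
- P = 10, D = 5: the average is 6.4 and 5.4, so the error changes sign.
- P = D: no error at any attendance.

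For scale, 1.5.6 takes 0 to 10 mmHg as the hypoxic range and reports baselines from about 1 to about 24 mmHg.

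With two pre-course sessions, w exceeds 28.6% only if a patient averages less than one on-course session a week. Any post-course sessions would add a third component to the mix.

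**The case against.** The strongest reply is that the averaging sentence is not the whole pO2 analysis. Section 7.1 also plans per-visit ANOVA and repeated-measures or mixed models, which need visit-level data. Course period can be worked out from visit and treatment dates. The progress report in 1.5.6 plots measurements one by one against days of implantation. This stands in large part: the pre-course to on-course contrast is not lost, and a careful analyst could recover it. It does not remove the point. The average is a stated rule for all subjects, the mixed models are introduced to handle differences across patients, and no analysis in 7.1 names a course period.

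Three stronger readings are tempting, and the documents do not support them.

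- A reader might take 39 measurements in 13 patients (39/13 = 3 each, 1.5.6) as typical and infer that two of three sessions, 67%, are pre-course. That needs a patient with a single on-course session in five weeks. The 39 measurements are not split by phase, and 1.5.3 reports more than 60 in all.
- A reader might infer that on-course values are further mixed because sessions fall before or after that day's fraction. Section 5.3 does say "Patients in Phase 1B will be receiving daily radiotherapy or a course of chemotherapy", and the only time item that 5.2.2 requires is session duration. But 5.2.2 defers detail to Standard Method 68.x. That document, the case report forms and the attachment on the measurement protocol were not supplied, so it cannot be said that the order goes unrecorded.
- A reader might infer that the trial's decisions are affected. They are not. The primary endpoint is device- or procedure-related toxicity of grade 3 or higher (3.2), the secondary endpoint is completion of planned measurements (3.3), and cohort expansion rests on adverse events (7.1).

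**Conclusion.** The concern holds as a minor point about one descriptive objective. Followed literally, 7.1 gives radiotherapy patients a pO2 average that is not the on-course level named in 2.2. About 29% of it is pre-course at one on-course session a week, falling to 7% at the ceiling of five. These shares assume two pre-course sessions, a 5-week course and no post-course sessions. The size in mmHg is unknown, because it scales with a treatment-related change that the documents do not report and that may be zero. A pooled average cannot show whether it is zero.

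**What to change.** In 7.1, for Phase 1B radiotherapy patients, replace the single average with room-air baseline pO2 summarised separately as pre-course, on-course and (if any) post-course, giving the number of sessions in each. Where a period has only one or two sessions, list the values. A course-period term may be added to the mixed model already planned.

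The change needs no visits or procedures beyond those planned, since 5.2.2 already separates the room-air baseline from the oxygen-breathing part of a session. The cost is precision per patient. With within-patient SD s and independent sessions, the standard error is s divided by the square root of the number of sessions:

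| Sessions (pre + on-course) | Pooled | Pre-course | On-course |
|---|---|---|---|
| 2 + 5 | s/√7 = 0.38s | s/√2 = 0.71s | s/√5 = 0.45s |
| 2 + 10 | s/√12 = 0.29s | 0.71s | s/√10 = 0.32s |
| 2 + 25 | s/√27 = 0.19s | 0.71s | s/√25 = 0.20s |

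The on-course summary loses little. The pre-course summary is imprecise because it rests on two sessions, which is why short periods are better listed.

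As a query only: confirm that Standard Method 68.x or the case report form records when a session took place relative to that day's fraction.

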## 7.2 Subject Population(s) for Analysis

The subject populations whose data will be subjected to analysis (both primary and secondary) include all evaluable participants in this Phase I trial.

---

 US Dept of Health and Human Services, Food and Drug Administration Center for Devices and Radiological Health. Center for Biologics Evaluation and Research. "Investigational Device Exemptions (IDEs) for Early Feasibility Medical Device Clinical Studies, including Certain First in Human (FIH) Studies: Guidance for Industry and Food and Drug Administration Staff". Document issued October 1, 2013.  
<http://www.fda.gov/MedicalDevices/DeviceRegulationandGuidance/HowtoMarketYourDevice/InvestigationalDeviceExemptionIDE/ucm162453.htm>.

Browne RH: On the use of a pilot sample for sample size determination. *Stat Med.* 1995, 14: 1933-1940.

Sim J, Lewis M: The size of a pilot study for a clinical trial should be calculated in relation to considerations of precision and efficiency. *J Clin Epidemiol.* 2012, 65: 301-308.

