## 3 Study Design

### 3.1 General Design

This is a Phase 1 clinical trial. Total enrollment will be 60 evaluable patients. Evaluable patients will be defined as patients who have the OxyChip implantation for the minimum of 3 days.

The study is split into Phase 1A (shorter duration of implantation with no other cancer therapy planned prior to excision) and Phase 1B (longer duration of implantation that is typically up to 12 weeks while receiving radiation therapy or longer if receiving neoadjuvant chemotherapy prior to surgical excision), as described below. OxyChip implant duration for both phases can be extended to 52 weeks (excluding the initial 6 evaluable patients in Phase 1A which may have the OxyChip implanted up to 4 weeks).

[figure not shown]
The initial 6 evaluable patients in Phase 1A will have the OxyChip placed for a short duration (up to 4 weeks) after which the OxyChip will be removed when the tumor mass is resected, prior to delivery of any further therapies. After successful implantation and removal of the OxyChip without any unacceptable toxicity in the first 6 evaluable patients, the Phase 1A cohort will be expanded to a total of 30 patients. In order to complete the safety and toxicity assessment of the short-term implantations, we will require that at least 3 patients have OxyChip implantations for a duration of at least 2 weeks, prior to proceeding to Phase 1B (long term implantation). This may require enrollment of additional patients in Phase 1A in order to meet this criterion. Phase 1B will consist of one cohort of 3 evaluable patients receiving chemotherapy treatment and one cohort of 3 evaluable patients receiving radiotherapy. Only after a full evaluation of the first 3 patients that underwent chemotherapy will additional patients receiving chemotherapy be enrolled. Similarly, only after a full evaluation of the first 3 patients that underwent radiotherapy will additional patients receiving radiotherapy be enrolled. The two cohorts of 3 patients in Phase 1B are independent of each other, so either of these cohorts may continue accrual after the initial 3 patients while the other is still accruing for the initial 3 patients. A total of 30 patients will be enrolled in Phase 1B. .

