### 3.2 Primary Study Endpoint

For the primary objective (*safety of the implantation procedure: the OxyChip itself and removal of the OxyChip is expected to be well-tolerated with minimal risk for complications*). The primary endpoints will be

all grade 3 or higher toxicities according to the Common Terminology Criteria for Adverse Effects (CTCAE) that are attributed to the device or procedure.

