### **4.4 Early Withdrawal of Subjects**

#### **4.4.1 When and how to withdraw subjects**

A subject may be withdrawn from the study at any time at the discretion of the treating physicians or if the patient withdraws consent. If the OxyChip was placed before withdrawal, there will be two options for withdrawing from the study, as follows:

1. Discontinuing the oxygen measurements: Repeated oxygen measurements will be stopped at the patient's request for any reason. The reason will be recorded and tracked as part of the study feasibility outcome. Under these circumstances, the OxyChip will not be immediately removed. Preferably, the OxyChip will be removed at the time originally planned when the tumor is resected.
2. Removal of the OxyChip: The OxyChip may be removed at any time at the patient's request. If the patient wishes to withdraw completely from the study, then the OxyChip will be removed. The OxyChip will also be removed early if there is an adverse event associated with the implant or if it is having (or may have) an adverse effect on the patient. This will require either surgical excision of the OxyChip or an en bloc surgical resection of the tumor with inclusion of the OxyChip. The type of surgery that is performed will be at the discretion of the surgical oncologist.

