### 8.2 Recording of Adverse Events

Clinical study subjects will be questioned about adverse effects at study visits. The visits will be documented in the clinical records. Adverse effects with suspected causal relationship to study procedures, determined by the PI or co-I, will be recorded on study adverse effects forms and summarized in CRFs.

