### **8.4 Stopping Rules**

The study will be stopped for any grade 3 or higher toxicity. The study will not re-open until the event is analyzed and deemed to be unrelated to the OxyChip or oxygen measurements.

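### The primary safety analysis is limited to patients with at least 3 days of implantation, so a grade 3+ toxicity that leads to earlier removal drops out of the primary result.

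*Combined protocol and SAP*

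**What the plan says.** Section 7.2 gives the only statement of who is analysed: "The subject populations whose data will be subjected to analysis (both primary and secondary) include all evaluable participants in this Phase I trial". The 3-day condition comes from section 3.1: "Evaluable patients will be defined as patients who have the OxyChip implantation for the minimum of 3 days". No safety set or all-implanted set is defined elsewhere.

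Section 3.2 defines the primary endpoint as "all grade 3 or higher toxicities according to the Common Terminology Criteria for Adverse Effects (CTCAE) that are attributed to the device or procedure". It sets no minimum time in place.

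Section 4.4.1 covers withdrawal after placement. The chip may come out whenever the patient asks, and: "The OxyChip will also be removed early if there is an adverse event associated with the implant". Section 4.1 (criterion 6) requires at least three days between implantation and planned excision, so any removal before day 3 is unplanned.

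Event capture does not depend on being evaluable. Section 8.2 states: "Adverse effects with suspected causal relationship to study procedures, determined by the PI or co-I, will be recorded on study adverse effects forms". Section 8.4 stops the study for any grade 3 or higher toxicity and adds: "The study will not re-open until the event is analyzed and deemed to be unrelated to the OxyChip or oxygen measurements".

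**The concern.** Whether a patient enters the primary analysis depends on something that happens after implantation, and the primary endpoint can itself bring it about. Section 2.1 puts the implantation procedure within the primary objective and lists bleeding, infection and allergic reaction among the effects to watch. An acute bleed or allergic reaction that leads to removal on day 0, 1 or 2 is the kind of event nearest to implantation, and it is the kind the primary result can omit. An attempt that fails to leave a chip in place gives zero days of implantation, so a toxicity from that attempt would also fall outside the set.

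This is a first-in-human device trial whose main product is a safety statement. At stake is whether that statement reads no events or one event, and over which denominator. Later planning would rest on it, since section 7.1 says the study is meant to help design a larger one.

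**Working it through.** **Following one patient through the text.** Suppose a grade 3 toxicity attributed to the procedure or chip occurs on day 1 and the chip is removed on day 2.

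| Step | Section | Result |
|---|---|---|
| Is it a primary endpoint event? | 3.2 | Yes; no minimum residence time |
| Does the plan provide for removal? | 4.4.1 | Yes; for an implant-associated event, or on request |
| Is the patient evaluable? | 3.1 | No; fewer than 3 days |
| Is the patient in the primary analysis? | 7.2 | No; evaluable participants only |
| Does another section put the patient back? | 4.4.2, 8.2, 8.3, 8.4 | No; these cover survival, withdrawal reasons, recording, reporting and stopping |

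A patient with the same event who keeps the chip for 3 days or more is analysed normally. The gap is confined to removal before day 3 and to failed placement.

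**The plan's own figure.** Phase 1A is 6 + 24 = 30 and Phase 1B is 30, so the total is 30 + 30 = 60, as stated. No toxicity rate, alpha, power or confidence interval is given for the primary endpoint, so there is no sample-size derivation to reproduce.

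**Size of the effect.** The event counts below are assumed. Intervals are exact (Clopper-Pearson) two-sided 95%. For 0 events in n, the upper limit is 1 − 0.025^(1/n). For x ≥ 1, the limits are the 2.5% quantile of Beta(x, n − x + 1) and the 97.5% quantile of Beta(x + 1, n − x).

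Worked example: for 0/60, 1 − 0.025^(1/60) = 5.96%. For 1/61 = 1.64%, the limits are 0.04% and 8.80%.

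| Scenario (one early event, all others event-free) | Section 7.2 as written | All implanted |
|---|---|---|
| (a) Chip-related event at the tenth implant; study stops | 0/9, upper limit 33.6% | 1/10 = 10.0% (0.3 to 44.5%) |
| (b1) Procedure-attributed event; study re-opens; accrual to 60 evaluable | 0/60, upper limit 6.0% | 1/61 = 1.6% (0.04 to 8.8%) |
| (b2) As b1, but the 30 + 30 enrolment totals bind | 0/59, upper limit 6.1% | 1/60 = 1.7% (0.04 to 8.9%) |
| (c) As b1, within one phase of 30 enrolled | 0/29, upper limit 11.9% | 1/30 = 3.3% (0.1 to 17.2%) |

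Scenarios (b) and (c) can arise because sections 3.2 and 8.4 differ in scope. The endpoint counts toxicity attributed to the device or the procedure, while the re-opening condition mentions only the OxyChip and the oxygen measurements. An event attributed to the procedure alone could therefore be followed by re-opening and full accrual.

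**Related wording.** Section 3.1 ties the Phase 1A expansion to successful implantation and removal "without any unacceptable toxicity in the first 6 evaluable patients". Section 7.1 bases progression on "the presence and severity of any unexpected adverse events and whether they can be attributed to the OxyChip", with no such restriction, and the Study Summary and section 1.6.1 likewise have none. The Study Summary and section 3.1 plan 60 evaluable patients, yet each phase is also totalled or capped at 30 enrolled. Both cannot hold if any enrolled patient proves not evaluable.

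**The case against.** **The event is not lost.** It is recorded, reported to the FDA and IRB if it meets their criteria, and it stops the study. This is correct, and it means the point is not about oversight. But none of those sections places the patient in the section 7.2 population.

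**The verb in section 7.2 can be read as non-exhaustive, and section 3.2 names no population.** That reading is possible. It would leave the denominator undefined rather than correct, because no other set is named.

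**Scenarios (b) and (c) need an unusual sequence.** An event judged implant-associated enough to prompt removal under section 4.4.1 is hard to call unrelated to the OxyChip under section 8.4, and section 8.3.1.3 classes questionable causality as device-associated for reporting. The clearest route is a purely procedural grade 3+ event with removal within two days at the patient's request. Section 4.4.1 also allows removal when the chip only may be having an adverse effect, so the sequence is uncommon but possible.

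**In scenario (a), nobody would publish a bare 0/9 from a trial halted by the excluded event.** Probably so, but the plan should not rely on authors departing from its stated population.

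**The cohort-gate wording is minor.** Largely true. In the section 3.1 schema, evaluable patients serve mainly to time the decisions, and section 1.6.2 reports no unacceptable toxicity in the first two Phase 1A cohorts. The gate wording and the 60-against-30 + 30 wording are secondary reconciliations.

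**Keeping the 3-day set for feasibility leaves a similar exclusion there.** This stands as a caution: measurements may start one day after implantation, so early removals should be shown beside the feasibility result.

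**Conclusion.** The concern holds. Sections 3.1 and 7.2 together make membership of the primary safety population depend on the outcome, and nothing else in the plan corrects this. One early event changes the reported result from none to one: on the assumed counts, 0% instead of 1.6% of all implanted at full accrual, or 0% instead of 3.3% within one phase of 30 enrolled. The intervals overlap widely, so the importance lies in the change of headline more than in the percentage.

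These figures assume one early event and none among other patients. They also assume that section 7.2 is applied literally and, for full accrual, that the study re-opens. The documents describe no such event: section 1.5 gives a maximum CTCAE grade of 1 to date. The fault is in the planned rule, not in observed data. It should be fixed, and doing so before any such event means the choice of population cannot appear to be driven by results.

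**What to change.** - In section 7.2, define the primary safety population as every patient in whom OxyChip implantation was attempted, whatever the time in place. Report the number of patients with at least one primary endpoint event over that denominator, by phase, with an exact 95% confidence interval.
- Keep the 3-day evaluable set for accrual counts and the secondary feasibility analysis. List beside the feasibility result any patient whose chip was removed before day 3, with the reason.
- Reconcile section 3.1 and its schema with section 7.1, the Study Summary and section 1.6.1, so that cohort reviews are stated to consider events in all implanted patients.
- Reconcile the 60 evaluable patients with the 30-per-phase enrolment totals.
- Sections 3.2 and 8.4 differ on whether procedure-attributed events are covered. They must be reconciled; which scope should apply is for the sponsor and investigators.

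The cost is a wording change in section 7.2 with matching edits in section 3.1 and its schema. No new patients or data are needed, because sections 8.2 and 8.3 already have these events recorded. The only downside is that the reported safety figure may be slightly less favourable.
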